**Secondary:**

- Comparison of primary and secondary efficacy parameters between doses
- Incidence of adverse events (AEs), serious adverse events (SAEs), and changes in laboratory test results
- Bone marrow improvement:

 
○ Bone marrow response rate at weeks 12, 24, and 36
 
○ Duration of bone marrow response
 
● Hemoglobin improvement
 
	
Baseline Status	Categories of Hemoglobin Improvement
Subjects who are transfusion dependent ( $\geq 2$ units PRBC every 4 weeks for 12 weeks prior to or after C1D1), regardless of baseline hemoglobin level	Percent of subjects with Red cell transfusion independence (no transfusions for $\geq 12$ consecutive weeks) OR 50% reduction in RBC transfusions for $\geq 12$ consecutive weeks
Subjects with baseline hemoglobin $< 100$ g/L AND Not transfusion dependent	Percent of subjects with $\geq 10$ g/L and $\geq 20$ g/L increase in hemoglobin for $\geq 12$ consecutive weeks without transfusions

 
● Platelet improvement:
 
	
Baseline Status	Categories of Platelet Improvement
Subjects who are transfusion dependent ( $\geq 2$ platelet transfusions in any 12 weeks prior to or after C1D1), regardless of baseline platelet level  Platelet transfusion = either 1 unit apheresed (single donor) platelets or 4-8 units pooled random donor platelets	Percent of subjects with: Platelet transfusion independence (no transfusions for $\geq 12$ consecutive weeks)  OR 50% reduction in platelets transfusions for $\geq 12$ consecutive weeks
Subjects with $25 < \text{baseline platelets} < 50 \times 10^9/\text{L}$  AND Not platelet transfusion dependent	Percent of subjects with: Doubling of baseline platelet count for $\geq 12$ consecutive weeks without platelet transfusions  OR Platelet count $> 50 \times 10^9/\text{L}$ for $\geq 12$ consecutive weeks without platelet transfusions
Subjects with baseline platelet count $< 25 \times 10^9/\text{L}$  AND Not platelet transfusion dependent	Percent of subjects with: Doubling of baseline platelet count for $\geq 12$ consecutive weeks without platelet transfusions  OR

	Platelet count > 25 x 10  /L for ≥ 12 consecutive weeks without platelet transfusions

 
Hematologic improvement:
 
	
Baseline Status	Categories of Hematologic Improvement

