Subjects with both Hemoglobin $< 100 \text{ g/L}$ and Platelets $< 50 \times 10^9/\text{L}$	Percent of subjects who have EITHER Hemoglobin improvement OR Platelet improvement as described above and no worsening of hemoglobin or platelets from baseline
Subjects with only Hemoglobin $< 100 \text{ g/L}$	Percent of subjects who have Hemoglobin improvement as described above  AND Did not develop platelets $< 50 \times 10^9/\text{L}$
Subjects with only Platelets $< 50 \times 10^9/\text{L}$	Percent of subjects who have Platelet improvement as described above  AND Did not develop Hemoglobin $< 100 \text{ g/L}$ or new transfusion dependence

- Symptom improvement:

- Percent of subjects with 25% and 50% reduction in MPN-SAF Total Symptom Score from baseline at Week 36
- Mean change from baseline in EORTC QLQ-C30 at 36 weeks
- Duration of all improvement parameters listed above
- Percent of subjects with complete response, partial response, clinical improvement, stable disease, and progressive disease according to IWG-MRT criteria (Tefferi 2013, APPENDIX B)

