##### **7.11.6. Response Assessments**

Subjects will be assessed for response at Cycle 2 through Cycle 9. Response Assessments are based on International Working Group-Myeloproliferative Neoplasms Research and Treatment (IWG-MRT) criteria, to measure the overall response rate (ORR), defined as a clinical improvement (CI), partial remission (PR), and complete remission (CR) according to the International Working Group (IWG) Criteria ([APPENDIX B](#)).

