## APPENDIX B: International Working Group (IWG) consensus criteria for treatment response in myelofibrosis with myeloid metaplasia\*

Response categories	Required criteria (for all response categories, benefit must last for ≥12 wk to qualify as a response)
CR	Bone marrow: * Age-adjusted normocellularity; <5% blasts; ≤grade 1 MF† and Peripheral blood: Hemoglobin ≥100 g/L and <UNL; neutrophil count ≥ 1 × 10  /L and <UNL; Platelet count ≥ 100 × 10  /L and <UNL; <2% immature myeloid cells‡ and Clinical: Resolution of disease symptoms; spleen and liver not palpable; no evidence of EMH
PR	Peripheral blood: Hemoglobin ≥100 g/L and <UNL; neutrophil count ≥1 × 10  /L and <UNL; platelet count ≥100 × 10  /L and <UNL; <2% immature myeloid cells‡ and Clinical: Resolution of disease symptoms; spleen and liver not palpable; no evidence of EMH or Bone marrow: * Age-adjusted normocellularity; <5% blasts; ≤grade 1 MF†, and peripheral blood: Hemoglobin ≥85 but <100 g/L and <UNL; neutrophil count ≥1 × 10  /L and <UNL; platelet count ≥50, but <100 × 10  /L and <UNL; <2% immature myeloid cells‡ and Clinical: Resolution of disease symptoms; spleen and liver not palpable; no evidence of EMH
Clinical improvement (CI)	The achievement of anemia, spleen or symptoms response without progressive disease or increase in severity of anemia, thrombocytopenia, or neutropenia§
Anemia response	Transfusion-independent patients: a ≥20 g/L increase in hemoglobin level   Transfusion-dependent patients: becoming transfusion-independent¶
Spleen response#	A baseline splenomegaly that is palpable at 5-10 cm, below the LCM, becomes not palpable** or A baseline splenomegaly that is palpable at >10 cm, below the LCM, decreases by ≥50%** A baseline splenomegaly that is palpable at <5 cm, below the LCM, is not eligible for spleen response A spleen response requires confirmation by MRI or computed tomography showing ≥35% spleen volume reduction
Symptoms response	A ≥50% reduction in the MPN-SAF TSS††

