It is underscored that the consensus definition of a CR bone marrow is to be used only in those patients in which all other criteria are met, including resolution of leukoerythroblastosis. It should also be noted that it was a particularly difficult task for the working group to reach a consensus regarding what represents a complete histologic remission.

‡Immature myeloid cells constitute blasts + promyelocytes + myelocytes + metamyelocytes + nucleated red blood cells. In splenectomized patients, <5% immature myeloid cells is allowed.

§See above for definitions of anemia response, spleen response, and progressive disease. Increase in severity of anemia constitutes the occurrence of new transfusion dependency or a  $\geq 20$  g/L decrease in hemoglobin level from pretreatment baseline that lasts for at least 12 weeks. Increase in severity of thrombocytopenia or neutropenia is defined as a 2-grade decline, from pretreatment baseline, in platelet count or absolute neutrophil count, according to the Common Terminology Criteria for Adverse Events (CTCAE) version 4.0. In addition, assignment to CI requires a minimum platelet count of  $\geq 25,000 \times 10^9/L$  and absolute neutrophil count of  $\geq 0.5 \times 10^9/L$ .

||Applicable only to patients with baseline hemoglobin of <100 g/L. In patients not meeting the strict criteria for transfusion dependency at the time of study enrollment (see as follows), but have received transfusions within the previous month, the pretransfusion hemoglobin level should be used as the baseline.

¶Transfusion dependency before study enrollment is defined as transfusions of at least 6 units of packed red blood cells (PRBC), in the 12 weeks prior to study enrollment, for a hemoglobin level of <85 g/L, in the absence of bleeding or treatment-induced anemia. In addition, the most recent transfusion episode must have occurred in the 28 days prior to study enrollment. Response in transfusion-dependent patients requires absence of any PRBC transfusions during any consecutive "rolling" 12-week interval during the treatment phase, capped by a hemoglobin level of  $\geq 85$  g/L.

#In splenectomized patients, palpable hepatomegaly is substituted with the same measurement strategy.

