2.2 EFFICACY ENDPOINTS

2.2.1 Primary Efficacy Endpoint

Stage 1:

The primary endpoint for Stage 1 is the Overall Response Rate (ORR). Response rate is defined as the percent of subjects with a response as per International Working Group-Myeloproliferative Neoplasms Research and Treatment (IWG-MRT) criteria (assessed by the investigator), is defined as either:

• achieving clinical improvement (CI), partial remission (PR), or complete remission (CR) at a post-baseline assessment of treatment response

OR

 having at least stable disease (SD) for three consecutive end-of-cycle response assessments (e.g. Day 1 of the subsequent cycle) in conjunction with improvement in the bone marrow fibrosis score (as determined by adjudicated review) relative to baseline by at least one grade at any time point during the period of stable disease.

Stage 2:

The primary endpoint for Stage 2 is the bone marrow response rate (BMRR). Response rate is defined as the percent of subjects with a reduction in bone marrow fibrosis by at least one grade according to World Health Organization (WHO) criteria (see Appendix D of the protocol) from baseline to any time during the study as determined by a central adjudication panel of expert hematopathologists, blinded to subject, treatment, and time of biopsy.

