The platelet improvement analyses will be presented by platelet levels (subjects with platelet <50 x10^9/L at baseline and subjects with platelet <25 x10^9/L at baseline)

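### Unit error in Protocol Appendix B: the platelet minimum for clinical improvement is printed as 25,000 × 10⁹/L, and the documents do not say what floor was used

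*Protocol*

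**What the plan says.** The footnote to the CI row in Protocol Appendix B ends with two extra conditions. The first is that "assignment to CI requires a minimum platelet count of" at least 25,000 × 10⁹/L. The second, in the same sentence, is a neutrophil count of at least 0.5 × 10⁹/L.

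The table that this footnote qualifies works on a different platelet scale. Complete remission requires "Platelet count ≥ 100 × 10 9 /L and <UNL". One route to partial remission repeats the floor of 100; the other requires "platelet count ≥50, but <100 × 10 9 /L and <UNL".

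Elsewhere the platelet endpoints use cuts of 25, 50 and 100 × 10⁹/L. For subjects starting below 25, one form of platelet improvement in the protocol is "Platelet count > 25 x 10 9 /L for ≥ 12 consecutive weeks without platelet transfusions". SAP Section 4.4.5 reports platelet improvement separately for "subjects with platelet <25 x10^9/L at baseline".

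CI is a counted outcome:
- Protocol Section 7.11.6 has Stage 2 response assessments "to measure the overall response rate (ORR), defined as a clinical improvement (CI), partial remission (PR), and complete remission (CR").
- SAP Section 2.2.1 counts a Stage 1 subject as a responder on "achieving clinical improvement (CI), partial remission (PR), or complete remission (CR) at a post-baseline assessment of treatment response".
- Protocol Section 3.2 lists as a Stage 2 secondary endpoint: "Percent of subjects with complete response, partial response, clinical improvement, stable disease, and progressive disease according to IWG-MRT criteria".

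The SAP invokes the IWG-MRT criteria but restates no platelet minimum for CI, and its appendices do not reproduce Protocol Appendix B.

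**The concern.** A lesser response category should not demand a far higher platelet count than complete remission. The printed figure does, and by a margin that only a unit slip explains. It is not background text. It helps to decide whether a subject with an anemia, spleen or symptoms response is recorded as CI or as stable disease.

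The region where a floor of this kind matters is one that the trial recruits from. Stage 2 admits subjects on platelets below 50 × 10⁹/L with no lower limit (Protocol Section 5.1.1), requires that at least half have baseline thrombocytopenia (Section 10.2), and defines a separate group below 25 (Section 3.2). The classification of a subject near or below 25 with, say, a symptoms response depends on what the floor is. Stage 1 response was assessed by the investigator (SAP Section 2.2.1), so an unclear criterion could be read differently between sites.

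**Working it through.** **Inputs** (all platelet figures in 10⁹/L)
- CI floor as printed: 25,000 (Appendix B, CI footnote).
- Complete remission and first partial-remission route: 100. Second partial-remission route: 50 (Appendix B table).
- Stage 2 eligibility cut: 50 (Protocol Section 5.1.1).
- Endpoint and subgroup cut: 25 (Protocol Section 3.2; SAP Section 4.4.5).
- Neutrophil floors: 0.5 for CI, 1 for complete and partial remission (Appendix B).

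**Step 1. Ratio of the printed floor to the other thresholds**
- 25,000 / 100 = 250 times the complete-remission floor.
- 25,000 / 50 = 500 times the second partial-remission floor and the eligibility cut.
- 25,000 / 25 = 1,000 times the cut used in the endpoints and subgroups.

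**Step 2. Can the floor be met?** Complete remission needs a count below the upper normal limit. The documents give no value for that limit. Assuming 350 to 450, the printed floor is 25,000 / 350 = 71 times to 25,000 / 450 = 56 times the limit. No subject would reach it.

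**Step 3. Unit conversion.** A count per microlitre × 10⁶ / 10⁹ gives the count in 10⁹/L. So 25,000 per microlitre is 25,000 × 10⁶ / 10⁹ = 25 × 10⁹/L. The printed expression is what results if a per-microlitre number is given a per-litre multiplier: a factor of 1,000.

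**Step 4. Internal comparison.** For neutrophils the CI floor is 0.5 / 1 = one half of the remission floor, so the lesser category has the lower bar. For platelets as printed, the order is reversed by a factor of 250. At 25 × 10⁹/L the CI floor would be 25 / 50 = one half of the lower partial-remission floor. This fits the converted value but does not prove it.

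**Step 5. Consequence of a literal reading.** CI could never be assigned. A subject with an anemia, spleen or symptoms response short of partial remission, and without progression, would fall into stable disease, which Appendix B defines as the residual category. Complete and partial remission would remain assignable.

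**Step 6. Weight of one reclassified subject.**
- Stage 2: 84 / 3 = 28 per arm, so one subject moves a CI rate by 1 / 28 = 3.6 percentage points.
- Stage 1: Protocol Section 5.1.1 gives 27 subjects and SAP Section 4.4.1 gives four groups, an average of 27 / 4 = 6.75. Group sizes are not stated. Assuming six or seven, one subject moves a group's response rate by 1 / 7 = 14 to 1 / 6 = 17 points, against a benchmark of 10%. This applies only to a subject who does not qualify by the marrow route as well.

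**The case against.** The strongest reply is that no competent assessor would take the figure at face value. The complete- and partial-remission floors stand in the same table, and the natural correction lands on a cut that the protocol already uses. This is largely right, and Protocol Section 1.5 supports it. It reports four IWG symptom responses in Stage 1 at 36 weeks, and under Appendix B a symptoms response is a route to CI. Two limits remain. We cannot see whether the Stage 1 version of Appendix B carried the same figure, and a report of symptom responses does not show which floor, if any, was used.

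Second, the reach is narrow. SAP Section 2.2.1 keeps another route to Stage 1 response: sustained stable disease with a marrow grade improvement. A subject denied CI could still qualify that way, and Section 1.5 lists 10 bone marrow responses beside the four symptom responses. The Stage 2 primary endpoint is marrow grade alone. Stage 2 IWG-MRT categories are summarised as percentages by visit (SAP Section 4.4.2), and the protocol's pairwise tests on secondary endpoints are unadjusted and to be read with caution (Section 10.6.1.3.4). All of this stands.

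Third, the correction comes late. SAP Section 1 says that separate Stage 1 and Stage 2 plans were signed before their primary database locks. They are not among the documents reviewed and may have stated a floor. Correcting Appendix B now changes no assignment already made. That is why the fix includes a check of the recorded assignments.

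Reliance on silent correction is still a weak control, because platelet units slip elsewhere. SAP Section 4.3 gives baseline platelet cuts in g/L, and Section 2.2.2 prints a threshold as 100^9/L.

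**Conclusion.** The printed CI platelet minimum is wrong as a unit: 250 times the complete-remission floor beside it, and 1,000 times the 25 × 10⁹/L cut used elsewhere. It sits in an operative criterion, nothing in either document overrides it, and the floor actually used is not stated.

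A reader might infer that no CI was ever assigned, that the reported Stage 1 response rates are therefore unsound, or that subjects below 25 × 10⁹/L were credited with CI because the floor was ignored. The documents support none of these. The Stage 1 symptom responses point away from literal use, the marrow route does not depend on CI, and no assignment is shown to have changed in either direction.

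The effect is confined to the CI component of the Stage 1 overall response rate and the Stage 2 secondary IWG-MRT categories, including their repeats on the extension population (SAP Section 4.8) where applicable. The Stage 2 primary bone marrow response rate is unaffected. The number of subjects affected is unknown. That the floor is unattainable rests on an assumed upper normal limit of 350 to 450 × 10⁹/L; the inconsistency with the other thresholds rests on no assumption.

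**What to change.** 1. Reconcile the CI figure in Appendix B with the other platelet thresholds. Conversion points to 25 × 10⁹/L (25,000 per microlitre). The sponsor should confirm the intended value against the criteria that Appendix B cites before it is changed.
2. State the confirmed floor in SAP Section 2.2, for both stages, and say what floor was used when CI was assigned in the data already analysed.
3. Program a check of each CI assignment, and of each anemia, spleen or symptoms responder recorded as stable disease, against the recorded platelet counts. List the discordant cases, and report the Stage 1 response rate and the Stage 2 IWG-MRT categories with and without them if there are any.

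The cost is one corrected figure, one or two sentences in the SAP and one listing. Appendix A schedules a complete blood count including platelets on Day 1 of each cycle and at Cycle 9 Day 29, and the Stage 1 schedules in SAP Appendix 5 also collect platelets at each cycle, so no new data are needed.

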**APPENDIX C: Proposed Revised World Health Organization Criteria for Primary Myelofibrosis****Major criteria**

1. Presence of megakaryocyte proliferation and atypia, usually accompanied by either reticulin and/or collagen fibrosis, or, in the absence of significant reticulin fibrosis, the megakaryocyte changes must be accompanied by an increased bone marrow cellularity characterized by granulocytic proliferation and often decreased erythropoiesis (ie, prefibrotic cellular-phase disease)
2. Not meeting WHO criteria for PV, CML, MDS, or other myeloid neoplasm
3. Demonstration of *JAK2617V\_F* or other clonal marker (eg, *MPL515W\_L/K*), or in the absence of a clonal marker, no evidence of bone marrow fibrosis due to underlying inflammatory or other neoplastic diseases

**Minor criteria**

1. Leukoerythroblastosis
2. Increase in serum lactate dehydrogenase level
3. Anemia
4. Palpable splenomegaly

---

Diagnosis requires meeting all 3 major criteria and 2 minor criteria.

Small to large megakaryocytes with an aberrant nuclear/cytoplasmic ratio and hyperchromatic, bulbous, or irregularly folded nuclei and dense clustering.

Requires the failure of iron replacement therapy to increase hemoglobin level to the polycythemia vera range in the presence of decreased serum ferritin. Exclusion of polycythemia vera is based on hemoglobin and hematocrit levels. Red cell mass measurement is not required.

Requires the absence of *BCR-ABL*.

Requires the absence of dyserythropoiesis and dysgranulopoiesis.

Degree of abnormality could be borderline or marked.¶

Secondary to infection, autoimmune disorder or other chronic inflammatory condition, hairy cell leukemia or other lymphoid neoplasm, metastatic malignancy, or toxic (chronic) myelopathies. It should be noted that subjects with conditions associated with reactive myelofibrosis are not immune to primary myelofibrosis and the diagnosis should be considered in such cases if other criteria are met,

**APPENDIX D: WHO Grading of Bone Marrow Fibrosis (EU Consensus Criteria)**

Grading	Description*
MF - 0	Scattered linear reticulin with no intersections (cross overs) corresponding to normal bone marrow
MF - 1	Loose network of reticulin with many intersections, especially in perivascular areas
MF - 2	Diffuse and dense increase in reticulin with extensive intersections, occasionally with only focal bundles of collagen and/or focal osteosclerosis
MF - 3	Diffuse and dense increase in reticulin with extensive intersections with course bundles of collagen, often associated with significant osteosclerosis

\*Fiber density should be assessed in hematopoietic (cellular) areas.

**APPENDIX E: International Working Group for Myeloproliferative Neoplasms Research and Treatment (IWG-MRT) Dynamic International Prognostic Scoring System (DIPSS) for primary myelofibrosis\***

The IWG-MRT Dynamic Prognostic Scoring System is based on 5 prognostic variables at presentation:

Prognostic Variable	Value		
	0	1	2
Age, y	≤ 65	> 65	
White blood cell count, x 10  /L	≤ 25	> 25	
Hemoglobin, g/dL	≥ 10		< 10
Peripheral blood blast, %	< 1	≥ 1	
Constitutional Symptoms, Y?N	N	Y	

The values for the prognostic variables are added together to produce a total score, and subjects are assigned to risk groups based on their score.

Risk Group	Number of Risk Factors
Low	0
Intermediate-1	1-2
Intermediate-2	3-4
High	5-6

(Passamonti, Cervantes et al. 2010) [A dynamic prognostic model to predict survival in primary myelofibrosis: a study by the IWG-MRT \(International Working Group for Myeloproliferative Neoplasms Research and Treatment\)](#). *Blood*. 2010;115:1703-1708.

**APPENDIX F: Eastern Cooperative Oncology Group Performance Status**

ECOG Performance Status*	Grade
0	Fully active, able to carry on all pre-disease performance without restriction
1	Restricted in physically strenuous activity but ambulatory and able to carry out work of a light or sedentary nature, e.g., light house work, office work
2	Ambulatory and capable of all self-care but unable to carry out any work activities. Up and about more than 50% of waking hours
3	Capable of only limited self-care, confined to bed or chair more than 50% of waking hours
4	Completely disabled. Cannot carry on any self-care. Totally confined to bed or chair
5	Dead

\*As published in Am. J. Clin. Oncol.

**APPENDIX G: Myeloproliferative Neoplasm Symptom Assessment Form(MPN-SAF)**

Myeloproliferative Neoplasm Symptom  
Assessment Form (MPN-SAF)  
and  
Myeloproliferative Neoplasms Symptom  
Assessment Form Total Symptom Score (MPN-SAF TSS)

Symptoms among the Myeloliferative Neoplasms (MPNs) are severe and are correlated with poor prognosis. The Myeloproliferative Neoplasm Symptom Assessment Form (MPN-SAF) and Myeloproliferative Neoplasms Symptom Assessment Form Total Symptom Score (MPN-SAF TSS) are currently the only two validated measures symptom burden specific to the Myeloproliferative Neoplasms. The MPN-SAF is a 27-item measure that utilizes the 10-item Brief Fatigue Inventory in conjunction with a 17-item assessment of disease symptoms specific to the Myeloproliferative Neoplasms.

In order to ease survey administration, the 10- MPN-SAF total symptom score (MPN-SAF TSS), was created which includes a one-item assessment of worst fatigue from the BFI and 9 items from the original MPN-SAF. This abbreviated measure only includes the most pertinent and representative of the MPN symptoms and is intended to be used either as a one-time assessment or as a 7-day diary. Both surveys have been validated in clinical setting to be administered during a routine office visit (see references and articles below).

